6 RESEARCH METHODS

6.1 Study Design

This will be a non-interventional multi-center cohort study of patients initiating inebilizumab conducted with secondary data sources in France, Germany, Italy, the Netherlands, and Spain. The study will be based on a cohort-event monitoring design to capture both drug utilization and selected safety outcomes in patients initiating inebilizumab. The proposed study design allows for an efficient initial descriptive evaluation of AESI.

The **study period** in individual countries will start on different dates, depending on the launching time of the drug (the earliest in the second quarter of 2022) (Table 1). The end of the study period will be also country-specific (the latest in December 2027) and will depend on the dates of data availability in individual data sources (different lag times and data release dates).

Table 1 Study periods, by country

	France	Germany	Italy	Netherlands	Spain
	SNDS/ NOMADMUS	GKV	RISM	PHARMO	SIDIAP
Launch date (quarter, year)	Q2, 2022	Q3, 2022	Q2 2023	Q3, 2023	Q2, 2023
Start of study period	May 2022	Aug 2022	May 2023	Aug 2023	May 2023
End of study period	Dec 2026	Dec 2026	Dec 2027	Dec 2026	Sep 2027
Study period duration (months)	57	54	56	41	53

Q2, 2nd quartile; Q3, 3rd quartile

The study population will be constituted by a cohort of adult female and male patients diagnosed with NMOSD with entry trigger by inebilizumab initiation.

[figure not shown]
The **index date** (Day 0) will be defined as the date of first treatment (date of administration/prescription/dispensation, depending on data available in selected data sources) (Figure 1). Patients initiating the treatment will be identified throughout the study period. After the index date, enrolled patients will be followed for 12 months or censored at end of study period or loss of follow-up (death, disenrollment/de-registering) whichever occurs first.

A **baseline period**, including any time from when data are available up to the index date, will be used to establish comorbidities and NMOSD-related clinical characteristics, whereas a short period of 6 months prior to or at index date will be used to determine previous immunosuppressive therapies.

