6.3.3 Treatment patterns

During follow-up, treatment patterns will be characterized in terms of dose, treatment duration, frequency of drug discontinuation, switching and use of add-on therapies. All patients included in the study will be deemed exposed (at least one inebilizumab treatment), but only those with complete 12-month follow-up will be considered in the evaluation of the treatment patterns as described below.

According to the product specifications, the 12-month follow-up will cover 3 potential inebilizumab administrations: initial intravenous (IV) infusion followed by a second

infusion 2 weeks later and a subsequent infusion 6 months after the first treatment (Figure 2A). The first and third infusion will be considered in defining inebilizumab treatment patterns.

Treatment duration will be the sum of days under inebilizumab exposure during the follow-up. Number of days under exposure will be calculated for the first and the third infusion as the difference between end date of inebilizumab exposure period and the administration/prescription/dispensation date (Figure 2B).

[figure not shown]
Inebilizumab complete **exposure period** will be assumed to last 180 days after drug administration/prescription/dispensation. The **end date of the exposure** period will be defined as the end of each inebilizumab exposure period within follow-up or the end date of follow-up if comes first (Figure 2B).

A patient will be considered to be in inebilizumab **continuous use** if no gap longer than 60 days occurs between the end date of the first inebilizumab exposure period and the beginning of the third (2B). **Temporary discontinuation** (intermittent users) will be defined in patients with gaps between inebilizumab exposure periods longer than 60 days but with a subsequent inebilizumab administration/prescription/dispensation during the follow-up. A patient will be defined as having **permanently discontinued** inebilizumab if no subsequent inebilizumab treatment is registered during the follow-up after the end date of the first inebilizumab exposure period.

Switchers will be a subgroup of patients who discontinue inebilizumab (temporarily or permanently) during the follow-up and have other NMOSD maintenance drug administered/ prescribed (Table 9) after the end date of inebilizumab exposure period (2C). The alternative NMOSD drugs will be described.

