6.4.1 France

The French National Health Data System (Système National des Données de Santé [SNDS])

SNDS is the largest and most comprehensive healthcare dataset available in Europe with a 10-year longitudinal follow-up for more than 65 million individuals (including 50 million adults), and is highly representative of the French residents, covering 99% of the total population (15). Individuals enter the data source once born within or immigrating to the specific geographical area, and exit the data source either at date of death, emigration, or ending their insurance.

SNDS contains anonymized administrative and healthcare claims data from the French national health care insurance system databases including main health care claims database, ie., French National health insurance information system (*Système national d'information interrégimes de l'Assurance maladie* [SNIIRAM]), hospital discharge summaries (*Programme de Médicalisation des Systèmes d'Information* [PMSI]), and national death registry (Centre d'épidémiologie sur les causes médicales de Décès) (16).

SNDS contains information on beneficiaries age, sex, region of residence, death date, complementary universal health coverage status, and all out-patient healthcare drugs including all reimbursed prescription drugs identified by their ATC code, the date of delivery, quantity, and brand name. Medical procedures performed on an out-patient basis or in a healthcare institution are identified by the common classification of medical procedures (*classification commune des actes médicaux*), laboratory procedures are identified by the clinical pathology test nomenclature (*nomenclature des actes de biologie médicale*), and paramedical or medical visits are identified by the general nomenclature of professional procedures (*nomenclature générale des actes professionnel*).

The French National Health Insurance Information System, SNIIRAM

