French MS Registry (Observatoire Français de la Sclérose en Plaques [OFSEP]) was established in 2003; it is a national register actively covering data from 36 centers corresponding to 42 databases, of which 2 contain exclusively NMOSD patients. The data is collected from participating centers using the European Database for Multiple Sclerosis software. OFSEP covers approximately 50% of the total MS population in France and holds data for approximately 55,000 patients in total. Of these, 23,000 patients have records after June 2013, when a minimal data threshold was established. OFSEP contains information such as personal and sociodemographic information, clinical, paraclinical (e.g., MRI), and therapeutic data (disease-modifying treatments). Access to the data is made directly via an application to the database: the National Coordination Center and the Scientific Board of the database evaluate the applications and the Steering Committee makes the final decision (17).

French NMOSD Registry

Nested within the OFSEP is a French NMOSD registry recruiting patients with NMOSD presentations in France (*Neuro-Optico-Myélite Aiguë de Devic et des syndromes neurologiques apparentés* [NOMADMUS]). The cohort was initiated in 2010 and gathers clinical, biological and imaging data (18). The patients are regularly tested for anti-AQP4 and anti-MOG, and all cases are reviewed by an expert committee (19).

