6.4.4 Italy

The Italian Multiple Sclerosis & Related Disorders Register (*Registro Italiano Sclerosi Multipla e Patologie Correlate* [RISM]) was officially established in 2015. As of February 2023, the register was actively covering 133 MS centers, corresponding to a total of 80,353 patients, of which 273 are diagnosed with NMOSD. Since July 2022, the

register comprises a module for the collection of information on NMOSD, and has projects dedicated to NMOSD patients (22). Nonetheless, data on NMOSD patients were collected previous to 2022, without a specific module implemented. The data are collected from participating centers through a web-based system developed for the study, available at the IMS&RD website. Data are collected from accrual to exit of database, which may occur at date of death, when patient moves to a center outside of the covered network or withdraws their consent to participate. The data are centrally monitored to ensure quality of data, completeness, accuracy, and consistence (23). Requests to access the data are evaluated by the Scientific Committee, composed by clinicians, methodologists, representatives of MS centers, and of the Italian Neurological Society (23).

To ensure the collection of sufficient data for the clinical characterization of the single patient mandatory variables collected by the register include patient identification, demographics, vital status, disease onset date, diagnosis date, relapses, treatments and severe adverse events. This minimum dataset may be completed with an extension to optional information on family history, comorbidities, laboratory tests and MRI. Furthermore, the register has data on patient's unique personal identifier, to avoid inclusion of the same patient by more than 1 center. Diagnosis information is available and captured with ICD-9-CM coding system.

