6.7.2.3 Objective 3: Incidence of AESI

The AESI evaluated in this study include the following categories: serious infections, opportunistic infections, hepatitis B reactivations, infusion related reactions, and malignancies. Analysis of AESI will include estimation of the cumulative incidence (i.e., risk), incidence rate, and time to AESI onset ([Table 5](#)). All analysis for AESI events (i.e., cumulative incidence, incidence rate and time-to-onset) will be performed using an intention-to-treat approach i.e., patients will be considered exposed regardless of subsequent discontinuation.

The cumulative incidence (with 95% CI) will be calculated separately for each AESI category considering the overall study population. For all AESI categories, except infusion related reactions, the cumulative incidence (with 95% CI) will be calculated as the total number of incident reports of AESI during the follow-up divided by the total number of patients. An algorithm to identify incident reports of AESI will be developed and described in the SAP. For infusion related reactions, the cumulative incidence (with 95% CI) will be calculated as the total number of all reports of infusion related reactions on the day of infusion (if date of inebilizumab administration is available) or during the first 3 days following prescription/dispensation (if date of inebilizumab administration is not available), divided by the total number of patients in the overall study cohort. Additional details of this calculation will be provided in the SAP.

The cumulative incidence estimates for each AESI category, except infusion related reactions, may also be calculated for shorter periods e.g., in monthly intervals after index date. In this case, the cumulative incidence in the first month after index date would consider patients with AESI reports in the first month in the numerator and patients with complete 12-month follow-up in the denominator. The cumulative incidence in the second month would consider patients with reports recorded only in the second month in the numerator and patients with complete 12-month follow-up included in the denominator. Due to the limited sample size, the time intervals may need to be clustered into e.g., 3-month intervals with the numerator and denominator adjusted accordingly. If sample size permits, the difference (with 95% CI) in cumulative incidence between 2 time periods of observation may be calculated.

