	Incidence rate	From index date to AESI end of follow-up or censor*	First malignancy	Overall population
	Time to event	From index date to AESI, end of follow-up or censor*	First malignancy	Overall population

* Censoring criteria will be the earliest of permanent treatment discontinuation, loss to follow-up (death, disenrollment/de-registering) or end of study period.

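### Loss to follow-up has no last-contact criterion, so Italian registry patients who lapse without a recorded exit count as fully followed and event-free, and often as permanently discontinued

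*Protocol*

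**What the plan says.** Protocol section 6.1 has patients "followed for 12 months or censored at end of study period or loss of follow-up (death, disenrollment/de-registering) whichever occurs first". The abstract and the Figure 1 footnote give the same list. The Table 5 footnote adds one item: "Censoring criteria will be the earliest of permanent treatment discontinuation, loss to follow-up (death, disenrollment/de-registering) or end of study period". The text of section 6.7.2.3 says instead that AESI analyses follow intention to treat, so that "patients will be considered exposed regardless of subsequent discontinuation". None of these places sets a last-visit, last-entry or minimum-activity criterion.

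The sources end observation differently. In the French claims system (SNDS), people "exit the data source either at date of death, emigration, or ending their insurance". RISM, the only Italian source, is filled by participating centres through a web system, and section 6.4.4 gives its exit events as "date of death, when patient moves to a center outside of the covered network or withdraws their consent to participate". No exit event is described for the French registry NOMADMUS.

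Section 6.3.3 classes a patient as having permanently discontinued "if no subsequent inebilizumab treatment is registered during the follow-up after the end date of the first inebilizumab exposure period". Section 6.7.2.2 uses patients followed for the full 12 months as the denominator. Section 6.7.2.3 divides AESI reports by all patients and carries patients without an AESI to the end of follow-up.

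**The concern.** The censoring list fits insurance data, where enrolment implies that reimbursed care will appear. In a centre-entered registry, a patient who stops attending, or whose centre stops entering data, meets none of the listed criteria. Missing data then turn into results: no treatment record becomes discontinuation (Objective 2), and no event record becomes event-free time (Objective 3). Results are reported by country and data source (section 6.7.1), so the Italian estimates would carry the bias undiluted. The limitations in section 6.9 do not mention registry inactivity; they present disease registries as a way to reduce incompleteness.

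**Working it through.** **The plan's own figure.** The protocol gives no lapse share, so there is no stated figure for this point. Its only size calculation, Table 3, reproduces: n = 1.96² × 0.01 × 0.99 / 0.01² = 380 (stated 380). This point does not change it.

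**Tracing one patient.** Take a RISM patient whose last entry is the day-14 infusion, with no exit recorded.

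- Censoring (6.1): no criterion is met, so follow-up is complete at 12 months.
- Treatment pattern (6.3.3, 6.7.2.2): no later infusion is registered, so the patient is permanently discontinued and in the denominator.
- Cumulative incidence (6.7.2.3): in the denominator, with no event possible after day 14. The short-interval estimates also use patients with complete follow-up, so the patient is in those denominators too.
- Incidence rate: credited with 365 days under the intention-to-treat text. Under the Table 5 footnote, credited with about 180 days, if discontinuation is dated at the end of the first 180-day exposure period.

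If the lapse comes after the third infusion is recorded, the discontinuation label does not arise, but unobserved time still counts as event-free.

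**Incidence rate.** Assumptions: a share s of registry initiators is silent after day 14; everyone else is observed for 365 days; the event rate is constant and low.

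Observed days per patient = 365(1 − s) + 14s.
Counted days, intention to treat = 365.
Counted days, footnote = 365(1 − s) + 180s.
Understatement = 1 − observed / counted.

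| s (assumed) | Observed | Counted, intention to treat | Understated | Counted, footnote | Understated |
|---|---|---|---|---|---|
| 10% | 329.9 | 365 | 9.6% | 346.5 | 4.8% |
| 20% | 294.8 | 365 | 19.2% | 328.0 | 10.1% |

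**Cumulative incidence.** The footnote does not apply. With risk spread evenly over the year, observed risk = r × (1 − s × 351/365). A true 1% is seen as 0.90% (s = 10%) or 0.81% (s = 20%); a true 4% as 3.62% or 3.23%. For scale, the protocol's 400 patients give 95% half-widths of 0.98 points at 1% and 1.92 points at 4%, so this shortfall lies within the planned imprecision.

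**Permanent discontinuation.** With true share d (also assumed), observed share = (1 − s)d + s.

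| True d | s = 10% | s = 20% |
|---|---|---|
| 5% | 14.5% | 24% |
| 10% | 19% | 28% |
| 20% | 28% | 36% |

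**Pooled.** Table 4 puts Italy at 36% of expected NMOSD patients (208/576 and 1,756/4,870). At that weight, a true 10% would be seen as 0.36 × 19% + 0.64 × 10% = 13.2%, or 16.5% with s = 20%. Section 6.4.4 counts only 273 NMOSD patients in RISM in February 2023, so its real weight may be smaller.

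**The case against.** Several counter-arguments have force.

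- **The SAP could settle it.** Section 6.7.1 leaves full variable definitions to the SAP, and recorded RISM transfers and consent withdrawals plausibly count as de-registering. The second part stands: only unrecorded lapses are missed. The first does not dispose of the point, because the protocol states the censoring list as complete and does not defer it.
- **The footnote limits the harm.** A reader might infer that every silent patient adds 12 false event-free months to the rate. The documents do not support that as the only reading: the Table 5 footnote would stop risk time at discontinuation, which roughly halves the rate bias. It does not touch cumulative incidence.
- **France is different.** A reader might treat NOMADMUS like RISM. Table 1 pairs it with SNDS, which has defined exits and captures inpatient diagnoses and expensive in-hospital drugs such as monoclonal antibodies. The problem reaches NOMADMUS only for patients not linked to SNDS; the protocol does not say whether patient-level linkage will be made.
- **The French MS registry count is not a lapse rate.** Of about 55,000 patients, the protocol says: "Of these, 23,000 patients have records after June 2013, when a minimal data threshold was established". One might read this as proof that silence is common. It reflects a 2013 data threshold in a mainly MS register and says nothing about lapse within 12 months of starting this drug.
- **Unobserved care is not confined to registries.** PHARMO's high-cost drug data cover just over half of hospitals, and SIDIAP has hospital linkage only for a subset. Country differences would therefore not be a clean registry effect.

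**Conclusion.** The gap is real and is clearest in RISM. The stated rule treats an unrecorded lapse as complete follow-up. The direction follows from the protocol's own definitions: discontinuation is biased upward and AESI incidence downward. The size is not known, since the silent share, its timing and the true discontinuation share are all assumptions here. On those assumptions, discontinuation is the more exposed result, with a true 10% appearing as 19% or 28% within the registry. The AESI rate is understated by 9.6% or 19.2% under the intention-to-treat text, and by 4.8% or 10.1% under the Table 5 footnote. The conflict between that text and that footnote must be reconciled in its own right. The documents do not show that lapse is frequent.

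**What to change.** In section 6.1, the Figure 1 footnote and the Table 5 footnote, for RISM and for NOMADMUS patients not linked to SNDS, end follow-up at the earliest of the existing criteria and the last recorded registry entry of any kind at data extraction. Any entry is a safer anchor than a visit date, because visit dates are not among the RISM mandatory variables listed in section 6.4.4. In section 6.3.3, do not assign permanent discontinuation from silence alone: require a recorded stop or a later entry showing no further infusion, and otherwise report the status as unknown. Report registry results under both the current rule and the last-entry rule. Reconcile the Table 5 footnote with the intention-to-treat text.

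The cost is wording plus one extra set of registry results. Fewer registry patients will count as complete, and person-time will be shorter. Censoring at the last entry may itself be informative: entries depend on treatment and events, and patients still receiving six-monthly infusions are more likely to have late entries, which could pull discontinuation downward. Reporting both ways exposes this but does not remove it.

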History of relapses will be ascertained depending on available data in the data sources (e.g., using documented relapse episodes as defined by individual disease-specific registries or considering the previous use of acute treatments such as intravenous corticosteroids, intravenous immunoglobulin or plasmapheresis therapy, or hospital admission with selected principal diagnoses) and will be defined in detail in SAP. Patients will be characterized according to the number of relapses in the previous 1 and 2 years (none, one, two or more).

Baseline use of **acute treatments** will include intravenous corticosteroids, intravenous immunoglobulin or plasmapheresis therapy in a 6-month period prior to the index date ([Table 7](#) NMOSD-Associated Conditions)

NMOSD-associated Conditions	Diagnosis ICD-9-CM Codes*	Diagnosis ICD-10-CM Codes*
Hypothyroidism	244.x	E89.0, E03.2, E03.8, E03.9
Pernicious anemia	281.0, 281.1	D51.x
Ulcerative colitis	556.x [excl. 556.2 and 556.3]	K51.xx [excl. K51.2x and K51.3x]
Myasthenia gravis	358.0x	G70.0x
Idiopathic thrombocytopenic purpura	446.6	M31.1
Hemiplegia/paraplegia	334.1, 342.x, 343.x, 344.0x-344.6x, 344.9	G11.4, G81.xx, G80.x, G83.0, G83.1x, G83.2x, G83.3x, G83.4, G83.9, G82.xx

NMOSD-associated Conditions	Diagnosis ICD-9-CM Codes*	Diagnosis ICD-10-CM Codes*
Bladder dysfunction	788.30, 788.31, 788.33, 788.34, 788.36, 788.37, 788.39-788.43, 596.xx	N30.xx, N31.x, N32.xx, N33
Neuropathic pain	353.x, 354.x, 355.x, 356.x, 357.x, 250.6, 729.2, 782	E08.40-E08.42, E09.40, E09.42, E10.40-E10.42, E11.40-E11.42, E13.40-E13.42, G50.0, G50.1, G54.x, G55.x, G56.x, G57.x, G58.x, G60.x, G61.x, G62.x, G63, G64, G65.x, G90.5x, M05.5x, M79.2, M54.1, R20
Antiphospholipid syndrome	289.81	D68.61
Sarcoidosis	135	D86.xx
Scleroderma	357.4, 359.6, 517.2, 701.0, 710.1	M34.xx, L90.0, L94.0, L94.1, L94.3
Sjogren's syndrome	710.2	M35.0x
Systemic lupus erythematosus	710	M32.xx
Dorsalgia	724.5	M54
Disorders of lipoprotein metabolism and other lipidemias	272.0, 272.1, 272.2, 272.3, 272.4, 272.5, 272.9	E78
Other acute disseminated demyelination	341.9	G36.9
Disorders of refraction and accommodation	367	H52
Visual disturbances	368	H53
Disturbances of skin sensation	782	R20
Somatoform disorders	300.81	F45
Other dorsopathies, not elsewhere classified	723.2, 723.3, 723.8, 723.9	M53

Abbreviations: ICD-9/ICD-10, 9th/10th Revision of International Classification of Diseases; CM, Clinical Modification; NMOSD, Neuromyelitis optica spectrum disorder

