*ICD-X-CM codes will be translated into local ICD-X codes and provided in SAP

Table 8 in Annex 3). To characterize **maintenance therapy** in the same period, the use of recommended drugs such as oral corticosteroids, immunosuppressants, B-Cell targeting therapies, tocilizumab, eculizumab, satralizumab (Table 9 in Annex 3) and other immunosuppressive treatments (Table 10 in Annex 3) will be retrieved.

The use of pain medications in the 6 months prior to the index date will be determined taking into account drugs specified in Table 11 in Annex 3.

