The use of **add-on therapies** will be identified by administration/prescription/dispensation of other NMOSD maintenance or other immunosuppressive drug(s) (Table 9 and Table 10) during any of inebilizumab exposure period (2D). Corticosteroid pre-medication before inebilizumab infusion (used to reduce potential infusion reactions) will not be considered as an add-on therapy.

Figure 2 Inebilizumab treatment patterns

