- Data sources relying on drug prescription/dispensation - and not administration - may result in exposure misclassification and bias in the treatment patterns characterization and time-to-event analyses. Additionally, reasons for treatment discontinuation, switching or augmentation are not possible to capture not allowing the documentation of changes in treatment.
- Some variables, such as drug dose, laboratory results of biomarkers and exams such as MRI may not be available in all data sources which will limit comparability and the ability of a more detailed characterization of inebilizumab users in those countries.
- Other variables, such as treatment indication, if not available in the data sources, will be based on pre-defined algorithms.
- The evaluation of drug safety using secondary databases does not allow for a causal assessment between inebilizumab exposure and the experienced outcome. NMOSD has been shown to be highly associated with other diseases including cancer (40). Additionally, an increased risk of malignancies or serious infections in NMOSD may be induced by the exposure to other immunosuppressive therapies (41,42). Please note, most malignancies have long latency periods in the absence of immunosuppression (43), and although immunosuppressive therapies possibly shorten the period (44), current study follow-up time may be too short (up to 1 year is the maximum) to identify some malignancies. Therefore, safety outcomes should be considered as signals of a possible safety concern of inebilizumab exposure.
- This study will capture safety outcomes that were serious enough to come to medical attention, which may underestimate the frequency of mild events. Additionally, misclassification is a possibility as it relies on the diagnosis codes. Identified serious infections, serious infusion related reactions or malignancies

represent a subgroup of all serious adverse events but for which the validity is expected to be higher.

- For some data sources, reporting of small numbers (e.g., <5) requires compliance with the local policies regarding data anonymization and the risk of patients' identification in observational research. For example, if a real value is 2, it may need to be presented as ≤ 4 in the results table. This may be a potential limitation for analyses that require stratification, such as the number of malignancies in a specific age groups. Furthermore, minimum and maximum values cannot be reported.

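### Previous immunosuppressive therapy is read from 6 months only, so agents last recorded earlier are tabulated as no previous therapy; the index day and steroid pre-medication are also not handled consistently at baseline

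*Protocol*

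**What the plan says.** Section 6.1 sets two look-back periods. The general baseline period is described as "including any time from when data are available up to the index date, will be used to establish comorbidities and NMOSD-related clinical characteristics". For earlier treatment the rule is narrower: "a short period of 6 months prior to or at index date will be used to determine previous immunosuppressive therapies".

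Section 6.3.2 applies the same length to the individual variables. Acute treatments are "intravenous corticosteroids, intravenous immunoglobulin or plasmapheresis therapy in a 6-month period prior to the index date". Maintenance therapy is to be characterised "in the same period, the use of recommended drugs such as oral corticosteroids, immunosuppressants, B-Cell targeting therapies" and further agents, using Tables 9 and 10. The same section lists previous acute and maintenance therapies among the NMOSD clinical characteristics, and classifies patients by number of relapses in the previous 1 and 2 years. Where a source has no documented relapses, they may be inferred by "considering the previous use of acute treatments such as intravenous corticosteroids, intravenous immunoglobulin or plasmapheresis therapy", among other options, with the detail left to the SAP.

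Steroid pre-medication is dealt with once, in section 6.3.3: "Corticosteroid pre-medication before inebilizumab infusion (used to reduce potential infusion reactions) will not be considered as an add-on therapy". Section 6.9 says that "an increased risk of malignancies or serious infections in NMOSD may be induced by the exposure to other immunosuppressive therapies".

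**The concern.** Previous immunosuppressive therapy is a named item of objective 1 in section 5, and many patients starting inebilizumab may have used another agent first. A 6-month window records whether a drug was used recently. It does not record whether the patient was treated before. A patient treated earlier than that appears as previously untreated, and the table cannot separate this patient from one who never received an agent. The same happens agent by agent: someone given an antibody nine months before index and oral steroids since would be tabulated as a steroid user only.

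The safety objective is affected through interpretation. Section 6.9 names other immunosuppressive therapies as a possible source of malignancies and serious infections, so a reader of the safety results needs the treatment history to put those events in context. The part of that history older than 6 months is not collected.

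The second part runs in the opposite direction. If the index day belongs to the window, or if pre-medication is recorded shortly before it, a steroid given because of the first inebilizumab infusion can be counted as baseline steroid use.

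**Working it through.** The protocol derives no figure from this window, so there is no stated number to reproduce. The check compares the rules and then gives one illustration.

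**Look-back by variable (sections 6.1 and 6.3.2)**

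| Variable | Look-back |
|---|---|
| Comorbidities, NMOSD characteristics | all available history |
| Relapses | 1 and 2 years |
| Acute treatments | 6 months, worded as before index |
| Maintenance and other immunosuppressive drugs | 6 months, the same period (6.3.2); before or at index (6.1) |

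Two inconsistencies follow.

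1. Section 6.3.2 places previous acute and maintenance therapies among the NMOSD clinical characteristics. Section 6.1 gives those characteristics full history, but gives previous immunosuppressive therapies 6 months.
2. Section 6.1 includes the index day and section 6.3.2 does not.

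**Do the data force 6 months?** Section 6.4 suggests not. SNDS has 10 years of longitudinal follow-up. The German claims go back to January 2008. SIDIAP began in 2006 with a mean follow-up of 10 years. PHARMO follows people for twelve years on average, and its high-budget-impact medication data run from 2017, against a Dutch study start of August 2023. In the Italian register, treatments are a mandatory variable. Any source that uses acute treatments as the relapse proxy will already need 24 months of those records for the 2-year count.

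**Share missed.** Tables 9 and 10 list the agents but give no dosing intervals, and the protocol gives no distribution of time since last dose. As an assumption, let the last dose fall evenly over the L months before index, with L at least 6. Everything older than 6 months is missed, so

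share missed = (L − 6)/L = 1 − 6/L.

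- L = 6: 1 − 6/6 = 0%
- L = 8: 1 − 6/8 = 25%
- L = 12: 1 − 6/12 = 50%
- L = 24: 1 − 6/24 = 75%

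The denominator is patients with an earlier agent whose last dose lies within L months. The range shows how much the answer depends on L, and it is not an estimate for this cohort.

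**Pre-medication.** Systemic corticosteroids carry the same ATC group, H02, in Table 8 (intravenous only) and Table 9 (oral). The exclusion in 6.3.3 covers add-on therapy, and no equivalent is written for either baseline variable. An index-day steroid record counts under the 6.1 wording and does not count under 6.3.2. A record dated before the index day counts under both.

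**The case against.** The best defence is that the study is descriptive. No comparator, adjustment or carry-over estimate is planned, and section 6.9 already rules out causal assessment and treats safety outcomes as signals. This limits the harm to description and interpretation. It does not make the description complete.

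A reader might go further in several ways that the documents do not support.

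- *The window contradicts the protocol's own exposure rule.* Section 6.3.3 says an inebilizumab exposure period "will be assumed to last 180 days after drug administration/prescription/dispensation" and tolerates a 60-day gap, so 180 + 60 = 240 days looks like the span of continuing treatment. But the gap is tolerated only when a further inebilizumab infusion follows. With none registered, the patient has permanently discontinued, and exposure ends at 180 days. A patient who left another agent resembles that second case, and 180 days is close to 6 months.
- *Long-interval agents drop out as a class.* Any dose within 6 months is captured. Only patients whose last record is older are lost.
- *The index day is definitely included.* Only 6.1 says so, which makes this an unresolved contradiction.
- *Pre-medication contaminates most baseline steroid data.* Its visibility is limited. SNDS holds in-hospital prescriptions only for expensive drugs, OFSEP's therapeutic data are described as disease-modifying treatments, SIDIAP uses prescriptions and pharmacy dispensing, PHARMO's inpatient pharmacy data cover about 10% of the Dutch population, and Table 8 has no OPS code for intravenous steroids.
- *Pre-medication will be counted as relapse.* The steroid proxy is one option among several and its definition is left to the SAP, so this is a risk to close off and not an error already made.

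The SAP may settle operational definitions and codes, but the length of the look-back is fixed in the protocol.

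**Conclusion.** The point holds as a limitation of a rule that the protocol fixes. Followed as written, objective 1 will understate earlier immunosuppression, because any agent last recorded more than 6 months before index is not listed. The safety results will be read without that history. The size is unknown: the illustration runs from 0% to 75% of patients with an earlier agent, and depends entirely on the assumed even spread and on L.

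Separately, 6.1 and 6.3.2 must be reconciled on the index day, and the pre-medication exclusion has a gap at baseline. That gap matters only where steroid administrations or dispensings around the infusion are recorded. The documents do not support a claim that safety estimates are biased by a stated amount, since no analysis uses previous therapy for adjustment.

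**What to change.** In sections 6.1 and 6.3.2:

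1. Report previous maintenance and immunosuppressive therapy over all available history, or over at least 24 months to match the relapse look-back. Give the last agent and the time since its last record.
2. Keep the 6-month result beside it, labelled *recent use*.
3. Flag patients whose recorded history is shorter than the chosen look-back as having incomplete history, so that absence of a record is not read as absence of treatment.
4. State in both sections that the baseline drug window ends on the day before index.
5. Extend the pre-medication exclusion to baseline corticosteroid use and, in sources where intravenous steroids serve as the relapse proxy, to that proxy.

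The cost is revised wording and a longer look-back in data that the sources already hold. The drawback is one more category, incomplete history, in the objective 1 tables, which may produce small cells under the masking rules in section 6.7.1.
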